Pediatric oncology patients represent a potentially excellent population on whom to base a herd immunity educational effort aimed at enhancing altruism in vaccine-hesitant parents: pediatric cancer patients tend to elicit strong sympathetic responses from the public; they come from all communities in the US and are therefore local; and they rely on herd immunity for protection from vaccine-preventable infections because they are largely unable to receive vaccines due to their immunocompromised state³³⁻⁴⁶. Therefore, we hypothesize that a brief educational encounter on herd immunity focusing on local pediatric cancer patients' risk and sponsored by local pediatric oncology providers will increase altruism scores and directly correlate with an increase in seasonal influenza vaccine acceptance. We aim to explore the overall effectiveness of this educational intervention, and also aim to explore whether there may be an identifiable subpopulation most amenable to this type of intervention based on baseline altruism score, race, educational level, or political affiliation.

Objectives

Specific Aim 1: To identify associations with influenza vaccine hesitancy, including parental demographics and altruism score, in families with healthy children attending two pediatric practices.

Specific Aim 2: In the cohort of families with baseline vaccine hesitancy, to assess the effectiveness of a pilot educational intervention focusing on the development of herd immunity for pediatric oncology patients by measuring:

- a. The change in vaccine hesitancy scores pre- and post-intervention.
- b. The change in the score of question number 6 on the Vaccine Hesitancy Scale, which uniquely and specifically relates to altruism. We will also compare the change in this individual score

with the change in the other individual question scores, which relate to other realms of vaccine confidence, including safety, efficacy, and trust.

c. The rate of influenza vaccine uptake compared to historic controls from previous influenza seasons.

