We will also conduct a retrospective chart review of all patients who participated in the initial survey to determine whether the child received the influenza vaccine. Retrospective chart review will also be conducted to estimate the influenza vaccine acceptance rates for each pediatrics practice over the same time period from one year prior.

Two study volunteers will be at each pediatric clinic. A volunteer will approach an eligible parent/guardian in the waiting room prior to their scheduled appointment and obtain informed consent to participate in the study. A consenting subject will complete the Vaccine Hesitancy Scale⁴⁷ orally with the study volunteer. The Vaccine Hesitancy Scale is positive if the average of all questions is greater than or equal to 3. When the study volunteer is inputting and grading the Vaccine Hesitancy Scale in a REDCap survey tool on an iPad, the subject will complete the Self-Report Altruism Scale⁴⁸ and several demographic questions on paper. If the guardian screens positive for vaccine hesitancy (i.e., vaccine hesitancy score average \geq 3), they will be given the informational handout along with a brief script. The parent will have the opportunity to review the intervention in the waiting room and during the visit while the provider is out of the room. If the guardian was deemed vaccine hesitant and was given the intervention, the study volunteer will remain at the nurse's station and wait for the visit to be completed. Once the family is finished, the study volunteer will approach the participant once again and complete the Vaccine Hesitancy Scale orally prior to check out. The subject's child's electronic health record will then be accessed to document whether that patient received the seasonal influenza vaccine that day.

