For Specific Aim 2, our primary outcome will be the change in vaccine hesitancy scores pre- and postintervention, which will be assessed with a paired t-test or Wilcoxon signed-rank test, following review of the score distribution. We will also measure the change in Question #6 (the only Altruism-specific question on the questionnaire) independently, and also compared with each other individual question on the questionnaire, and pre- and post-intervention change will be assessed with a paired t-test or Wilcoxin signranked test, following review of the score distribution. As a secondary outcome, the rate of influenza vaccine uptake will be compared qualitatively to historic controls.

For the Exploratory Aim, we will capture qualitative data and seek trends. No statistical computation will be done on these data.

All data will be entered directly into a Research Electronic Data Capture database and analyzed using SAS v9.4 (Cary, NC).

Human Subjects Protection

Risks for participation are not more than minimal. There is risk of accidental unauthorized release of identifiable personal information. Data access will be limited to study staff. Data and records will be kept locked and secured, with any computer data password protected. Participation in a post-study interview by the study volunteers will not require written consent, but it is voluntary. The grading for the elective course is Pass/Fail, and will be exclusively based on their participation in the actual study, and not the post-study interview, which is voluntary.

Subject Recruitment Methods

All parents who present to either pediatric clinic with children 6 months and up who are eligible for the flu vaccine will be eligible to participate in the study. Two student volunteers will be at each clinic for the recruitment process during flu season (between October and December depending on volunteer schedule availability). A volunteer will approach any parent(s) in the waiting room prior to their schedule appointments to recruit for the study regardless of gender or race/ethnicity.

For the retrospective chart review, there is minimal risk involved to participants. All protected health information will be de-identified prior to data analysis and publications; subject identity will be known only to the study staff. Subjects who participated in the initial arm of the study will be included in the chart review to determine further demographic data and whether the child received the flu vaccine.

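### Aim 2c does not say which of two descriptions of vaccine uptake it uses, and its historic comparator is a whole-practice rate with no stated numerator or denominator

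*Combined protocol and SAP*

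**What the plan says.** Four parts of the combined protocol and SAP bear on uptake.

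- **Objectives, Specific Aim 2.** The aim is set "In the cohort of families with baseline vaccine hesitancy". Item c is "The rate of influenza vaccine uptake compared to historic controls from previous influenza seasons".
- **Interventions and Interactions.** The overview plans a "retrospective chart review of all patients who participated in the initial survey to determine whether the child received the influenza vaccine". It also plans a chart review to "estimate the influenza vaccine acceptance rates for each pediatrics practice over the same time period from one year prior". Later in the section, directly after the post-intervention survey, the step-by-step procedure has the child's record accessed "to document whether that patient received the seasonal influenza vaccine that day".
- **Subject Recruitment Methods.** Everyone in the initial part of the study enters the chart review "to determine further demographic data and whether the child received the flu vaccine". Again there is no window. Recruitment runs between October and December.
- **Analytical Plan.** As a secondary outcome, "the rate of influenza vaccine uptake will be compared qualitatively to historic controls".

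Inclusion requires the child to be eligible for influenza vaccine. The examples of ineligibility concern age under 6 months and immune status, and the list is open-ended. A dose already received that season is not mentioned either way.

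**The concern.** Two analysts could each follow this text and report different uptake rates, one counting only doses given at the study visit and the other counting any dose found in the chart. Either rate would then be set beside a practice figure whose construction is not described. The historic figure also covers every family in the practice, whereas Aim 2c concerns the hesitant ones.

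Uptake is the only behavioural outcome in the study, and the protocol title is about raising uptake. Because the comparison is qualitative, readers will see bare percentages with no interval or test. A difference produced by definitions could then pass for an effect, or hide one.

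**Working it through.** **No figure to reproduce.** The documents state no uptake rate, expected or historic, and no share of children vaccinated before the visit. What can be checked is how far the definitions can diverge.

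**Inputs (assumptions, not from the documents).** Let *v* be the share of enrolled children already vaccinated that season, taken as 0, 10% and 40%. Let *q* be acceptance at the visit among the rest, taken as 30%.

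**Formulas, all enrolled children in the denominator.**

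- Visit-day rate = (1 − v) × q
- Vaccinated by the end of the visit = v + (1 − v) × q
- Gap = v, whatever the value of q

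| v | Visit-day rate | By end of visit | Gap |
|---|---|---|---|
| 0 | 30% | 30% | 0 points |
| 10% | 0.90 × 0.30 = 27% | 0.10 + 0.27 = 37% | 10 points |
| 40% | 0.60 × 0.30 = 18% | 0.40 + 0.18 = 58% | 40 points |

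The gap simply restates *v*, so the table shows sensitivity and is not an estimate. Against the 312 hesitant subjects in the sample-size section, 10% is about 31 children (0.10 × 312) and 40% about 125 (0.40 × 312). At v = 0, only vaccination after the visit can separate the two measures.

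**Direction against the historic rate.** Suppose behaviour is identical in both years, with the same *v* and *q*, so that a fair comparison shows no difference. For v = 10% to 40%:

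| Study measure | Historic rate built as | Apparent difference |
|---|---|---|
| Visit-day, 27% to 18% | Vaccinated by the end of the visit, 37% to 58% | Study lower by 10 to 40 points |
| Visit-day, 27% to 18% | Acceptance at the visit among those not yet vaccinated, 30% | Study lower by 3 to 12 points |
| Visit-day, 27% to 18% | Doses at the visit over all children seen | None |
| By end of visit, 37% to 58% | Doses at the visit over all children seen | Study higher by 10 to 40 points |

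The wording allows each of these, so the sign of any bias cannot be fixed from the documents.

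**Hesitant families against the whole practice.** Take the plan's own 25% baseline hesitancy as the share of hesitant families in the practice. The practice rate is then 0.25 × (hesitant uptake) + 0.75 × (non-hesitant uptake). The practice rate minus the hesitant rate equals 0.75 × (non-hesitant uptake − hesitant uptake). Unless the two groups take up vaccine equally, the hesitant cohort differs from the practice before any intervention, and one common uptake window does not remove this.

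**Comparator period.** The objective refers to earlier seasons in the plural, while the chart-review plan covers a single prior year. These need reconciling.

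**The case against.** A reader might infer more than the text supports: that already-vaccinated children are counted as refusals, that the comparison is therefore biased against the intervention, and that the two definitions lead to opposite conclusions. The case against that reading is sound on several counts.

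- **Eligibility.** A child who has had this season's vaccine may reasonably be regarded as no longer eligible for it, and the exclusion list is open-ended. Such children may never be enrolled. The documents do not settle this: the listed examples are about age and immune status, and no check of vaccination status before enrolment is described. The point stands as an ambiguity.
- **One definition, stated twice.** The visit-day sentence could simply make the earlier overview specific. That is possible. However, Subject Recruitment Methods repeats the version without a window, for everyone surveyed, and the Analytical Plan does not choose. The chart-review sentence also does not say that any dose at any time counts; it just gives no window.
- **Comparator.** An acceptance rate across visits would match a visit-day measure. This stands, and it removes any claim about direction.
- **Size.** The 10 to 40 points are the assumed share and nothing more, and zero belongs in the range. This stands.
- **Role.** The outcome is secondary and qualitative, with no test, alpha or power attached. This stands, so no formal conclusion can be reversed.

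What remains is that the plan names two measures, does not choose between them, and compares the result with a rate on an unstated basis in a different population.

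**Conclusion.** The point holds as a defect in the definition of a secondary outcome and is worth correcting. The Aim 2c rate is not tied to either description of uptake, and the historic rate has no stated numerator or denominator. It also covers whole practices, while the aim covers hesitant families.

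The divergence between a visit-day rate and a rate by the end of the visit equals the share of enrolled children already vaccinated that season. That assumes such children are enrolled and kept in the denominator. It is 0 points if none are enrolled and, illustratively, 10 to 40 points for shares of 10% to 40%.

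The documents do not support saying that already-vaccinated children are counted as refusals or that the bias runs against the intervention. The first needs three unstated conditions: that they are enrolled, that the visit-day record is the outcome, and that they stay in the denominator. The second also needs a historic rate built as coverage. Neither primary outcome is affected; what is limited is the interpretation of Aim 2c.

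**What to change.** 1. State one uptake definition and apply it to both years. From the chart reviews already planned, take as denominator the children with no dose recorded that season before the index visit, and as numerator receipt at that visit. Add receipt by a fixed, named date as a second measure.
2. State whether children already vaccinated that season may be enrolled. If they may, report their number and leave them out of this denominator.
3. Abstract the historic controls in the same way, from visits in the same calendar window, with a rule for choosing one index visit per child.
4. Reconcile the single prior year in the chart-review plan with the plural seasons in the objective.
5. Report uptake for all surveyed families beside the historic rate, since both then cover hesitant and non-hesitant families. Show the hesitant-only rate descriptively and do not read its comparison with the practice rate as an intervention effect.

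The cost is protocol wording plus abstraction of dose dates, for the study children and the historic sample, within reviews already planned. The outcome remains secondary and qualitative, and a historic comparison cannot separate the intervention from other changes between years.

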Exploratory Aim: In an effort to further understand the complex interaction between study volunteers (interviewing medical students) and study subjects, including how unique interactions between the study representative(s) and the study subjects may affect questionnaire responses and vaccine acceptance decisions, we aim to conduct motivational interviews with 20 vaccine-hesitant participants, and with four study volunteers. Each motivational interview will be conducted by [name], PhD, Associate Professor and Chair of the Department of Communication at Wake Forest University.

We aim to explore the relationship between baseline influenza vaccine hesitancy rates and baseline altruism scores. Effectiveness of our intervention is dependent on parental altruism levels; therefore, we also seek to determine if there is an association between parental altruism and vaccine hesitancy for their children.

Methods and Measures

Setting:

Study subjects will be recruited from two Wake Forest University Baptist Medical Center general pediatric practices: Westgate Pediatrics and Pediatrics - Ford, Simpson, Lively, and Rice. Westgate Pediatrics is located at [name]. Westgate serves a diverse population, with approximately 50% of patients receiving Medicaid services. Pediatrics - Ford, Simpson, Lively, and Rice is located at [name]. This latter practice serves a large population that is generally of a higher socioeconomic status than Westgate Pediatrics, with approximately 25% of patients receiving Medicaid services. Study volunteers will be Wake Forest School of Medicine medical students in their 4th year who volunteer to participate in this project as credit for a 4th year elective rotation.

Design:

A single-arm prospective cohort study will be conducted. The study will enroll as study subjects legal guardians of children who are influenza vaccine-eligible to measure their vaccine hesitancy scores, altruism scores, and the impact of an educational intervention focused on herd immunity on the guardians' vaccine hesitancy score.

Inclusion Criteria:

All legal guardians of children aged 6 months and up who are influenza vaccine-eligible and present to the pediatric clinic.

Exclusion Criteria:

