Legal guardians of children who are not influenza vaccine-eligible including children less than 6 months of age, children on immunosuppressive medications, and children with underlying medical conditions resulting in an immunocompromised state.

Sample Size:

Specific Aim 1: baseline vaccine hesitancy is 25%⁴⁷. Clinically meaningful difference in hesitancy is defined as 15%. This difference can be detected with 80% power with 250 subjects per group.

Specific Aim 2: We anticipate our intervention could reduce vaccine hesitancy from the national baseline of 25% to 15% on the post-intervention survey. Identifying this reduction from 15% to 15% in paired proportions with 80% power requires enrollment of 312 subjects who complete both tests (i.e. enrolling 312 subjects identified as vaccine-hesitant).

Exploratory Aim: Motivational interviews with study subjects (20) and study volunteers (4) will not be powered or statistically analyzed.

Interventions and Interactions

We will conduct a prospective cohort study of families with children aged 6 months and up who are eligible to receive the seasonal influenza vaccine. Subjects who consent to this study will answer questions which will include demographic questions, a baseline 20-item Altruism Scale, and an 8-item Vaccine Hesitancy Scale. The 20-item Altruism Scale will be scored based on a 5-point Likert scale, with each question scoring from 1-5, then added together to give a cumulative score. Higher scores indicate higher altruism. The Vaccine Hesitancy Scale will be scored as previously described: scoring responses for each item will be scored as follows: strongly agree = 1, agree = 2, disagree = 4, and strongly disagree = 5, such that higher values always indicated greater hesitancy. We will then calculate the average score of the 8 items included in the scale, and use the pre-defined average score of ≥ 3 as "hesitant." Subjects identified as vaccine-hesitant based on a Vaccine Hesitancy Score ≥ 3 will be given an educational handout and provided a standardized, brief educational session overviewing the educational handout. At the end of the doctor's visit, subjects will complete a second identical 8-item Vaccine Hesitancy Scale.

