Following study volunteer participation and subject participation in the study, up to four study volunteers and up to 20 vaccine-hesitant study subjects will be contacted by [name], PhD, to request an interview. The interviews will take place virtually, by phone or video, by [name]. Study subjects will have already provided written consent to this interview, but [name] will review the purpose of this phone call and provide an opportunity for study subjects to opt out. All study volunteers will be provided a Study Information Sheet when they orient as study volunteers on this project, which details the purpose of the research project and that up to four of the volunteers, [name] will review/re-provide a Study Information Sheet, detailing the purpose of the interview, but there will be no written consent for the study volunteers.

Analytical Plan

For Specific Aim 1, our primary outcome is vaccine hesitancy, which is dichotomized as hesitant (mean score \geq 3) or not hesitant (mean score \leq 3) based on results of the Vaccine Hesitancy Scale. Exposures will

include general demographic and clinical characteristics along with the Self-Report Altruism Scale (expresses as a continuous score from 20 to 100). The children's clinical status will be categorized using the Pediatric Medical Complexity Algorithm v3.1⁴⁹. Results will be analyzed initially using descriptive statistics to determine the prevalence of hesitancy. Associations between hesitancy and potential exposures will be assessed using chi square or ANOVA. Associations found to be statically significant in the bivariate analysis will be incorporated into a mixed-effects multivariable logistic regression model, which will treat practice location as a random effect. A p value of 0.1 will be used for inclusion of variables in the model; otherwise, a p value <0.05 will be the cutoff for statistical significance.

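### Aim 1 treats practice as a random effect with only two practices: its variance has one degree of freedom, is often estimated as zero, and adjusts for practice only in part

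*Combined protocol and SAP*

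**What the plan says.** The Objectives state Specific Aim 1 as: "To identify associations with influenza vaccine hesitancy, including parental demographics and altruism score, in families with healthy children attending two pediatric practices". The Setting section confirms the number of sites: "Study subjects will be recruited from two Wake Forest University Baptist Medical Center general pediatric practices". It describes the two as different. Of the first it says "Westgate serves a diverse population, with approximately 50% of patients receiving Medicaid services"; the second is "generally of a higher socioeconomic status than Westgate Pediatrics, with approximately 25% of patients receiving Medicaid services".

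The Analytical Plan for Aim 1 dichotomizes hesitancy, tests each exposure singly, and carries those that pass into a "mixed-effects multivariable logistic regression model, which will treat practice location as a random effect". The entry rule is: "A p value of 0.1 will be used for inclusion of variables in the model".

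The only software detail is SAS v9.4. The plan names no estimation method, gives no rule for a variance estimate of zero, and has no fixed-effect alternative or sensitivity analysis. It does not say whether the random effect is meant to control confounding by practice or to allow for clustering.

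**The concern.** A random effect treats the practices as draws from a population and estimates the spread of that population from the practices observed. With two, the spread rests on 2 − 1 = 1 degree of freedom. Two things follow.

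- When the practice difference is small to moderate, the variance estimate is often exactly zero. The fitted model is then ordinary logistic regression with practice left out.
- When the estimate is above zero, the practice difference is shrunk toward zero, so adjustment is partial.

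This matters here because Aim 1 is about demographic associations and the practices differ in socioeconomic mix. How far the reported odds ratios are adjusted for practice would depend on a poorly determined variance, not on a prior decision.

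A secondary point arises in the same paragraph. Aim 1 names the altruism score, but that score reaches the multivariable model only if its bivariate p value passes 0.1. It may therefore receive no adjusted estimate.

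**Working it through.** **The plan's own figure.** Sample Size, Aim 1 says: "This difference can be detected with 80% power with 250 subjects per group". For 25% versus 15%, two-sided 0.05, 80% power:

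n = [1.960·√(2·0.20·0.80) + 0.842·√(0.25·0.75 + 0.15·0.85)]² / 0.10² = 249.98, so 250 per group.

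The figure reproduces. It does not involve the practice effect, and the groups are not defined, so 250 per practice is an assumption below. Aim 2 needs "enrolling 312 subjects identified as vaccine-hesitant"; at 25% hesitancy that is 312 / 0.25 = 1,248 guardians, or 624 per practice if split equally. Both sizes are used.

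**Assumptions.** One binary exposure held by 50% and 25% of guardians in the two practices (as for Medicaid); no true exposure effect; about 25% hesitant. The documents give no practice odds ratio (OR), so 1.2, 1.5 and 1.9 were tried.

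**Hand approximation.** Let Z be the practice log odds ratio divided by its standard error. With two equal practices, the maximum-likelihood (ML) variance is zero when Z² < 2, and otherwise the fraction 2/Z² of the practice effect is left unadjusted. For a REML-type fit, replace 2 by 1. With no practice effect, P(χ²₁ < 2) = 84% and P(χ²₁ < 1) = 68% of fits give zero.

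The exposure–practice R² is 0.0625² / (0.375·0.625·0.25) = 0.067. At 250 per practice, SE = √[2/(250·0.25·0.75)] / √(1 − 0.067) = 0.214. At OR 1.5, mean Z = 0.405/0.214 = 1.90, so P(|Z| < 1.414) = 31%. The expected share left unadjusted is 45%.

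**Simulation.** 2,000 data sets per setting. ML used numerical integration over the random intercept; the REML-type fit was linearized pseudo-likelihood. Bias is the excess over the fixed-effect fit, in log odds. Shares are of the unadjusted confounding, which is 0.048 / 0.109 / 0.172 at 250 per practice and 0.047 / 0.107 / 0.167 at 624.

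| Per practice | Fit | Variance zero, OR 1.2 / 1.5 / 1.9 | Leftover bias | Share left |
|---|---|---|---|---|
| 250 | ML | 71 / 33 / 6% | 0.033 / 0.050 / 0.041 | 68 / 46 / 24% |
| 250 | REML-type | 52 / 17 / 2% | 0.021 / 0.028 / 0.021 | – |
| 624 | ML | 57 / 6 / 0.1% | 0.028 / 0.026 / 0.016 | 60 / 25 / 10% |
| 624 | REML-type | 38 / 2 / 0% | 0.017 / 0.013 / 0.008 | – |

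The Monte Carlo SE of the bias is at most 0.001. The 33% and 46% at OR 1.5 (250, ML) agree with the hand values of 31% and 45%.

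The sampling SD of the exposure log odds ratio is about 0.22 (250) and 0.14 (624). False-positive rates, ML random effect versus fixed effect, are 6.2 / 7.4 / 6.2% versus 5.5 / 6.0 / 5.4% (250) and 5.3 / 6.3 / 5.5% versus 4.9 / 4.8 / 4.7% (624), with a Monte Carlo SE of about 0.5 points.

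**Sensitivity.** With a real exposure effect (log odds 0.5), 250 per practice and 300 data sets per setting, ML gave zero variance in 60 / 30 / 4 / 0% at practice OR 1.25 / 1.5 / 1.9 / 2.5, and leftover bias of 0.036 / 0.048 / 0.037 / 0.024. With practices drawn from a normal distribution of SD 0.5, the variance was zero in 31% of fits and the estimated SD ranged from 0 to 0.69 (5th to 95th percentile).

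**Altruism screen.** Noncentrality is d·√[n₁n₂/(n₁+n₂)], tested at two-sided 0.1. For 125 hesitant versus 375 not (25% of 500) and d = 0.1, it is 0.968 against a critical value of 1.648, so the score misses entry in 75% of studies. For 312 versus 936 the miss rate is 55%. At d = 0.2 the rates are 39% and 8%. The values of d are assumptions.

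**The case against.** The strongest reply is that little changes in practice. The largest leftover bias, 0.050 log odds, is under a quarter of the sampling SD (0.050/0.22 = 0.23). At 624 per practice it is 0.028 or less under ML and 0.017 or less with a REML-type fit. At OR 1.2 the random effect even has slightly lower root mean squared error (RMSE) at 250 per practice, 0.221 versus 0.227. Zero estimates cluster where there is little to adjust: at OR 1.9 with 624 per practice, ML removes about 90% of the confounding. The larger sample may well be the realistic one, since all consenting guardians complete the Aim 1 instruments. The simulation also assumes a direct practice effect and a single covariate, whereas the plan would enter demographic variables that absorb part of it. All of this stands, and it limits the size of the problem.

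It does not rescue the random effect. Two practices say almost nothing about a population of practices, so neither clustering nor wider generalization is served, and a fixed term adjusts fully for practice.

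On altruism, it is fair that the score still gets its bivariate test and that the aim speaks of identifying associations. The screen is a separate and secondary matter.

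**Conclusion.** The concern holds. The single degree of freedom follows from the text and needs no assumption. Frequent zero estimates apply to small or moderate practice effects: up to an odds ratio of about 1.5 at 250 per practice, but only near 1.2 at 624. The resulting bias is at most about 0.05 log odds in the settings tried, so this does not invalidate Aim 1. The sizes rest on assumed practice odds ratios, exposure prevalences borrowed from the Medicaid shares, an assumed number per practice and an unstated estimator. The change should be made because it is nearly free and settles in advance whether the odds ratios are adjusted for practice.

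**What to change.** In the Analytical Plan for Specific Aim 1, replace the mixed-effects model and its entry rule with:

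> Hesitancy will be analyzed by multivariable logistic regression with practice location as a fixed two-level covariate. Practice and the Self-Report Altruism Scale score will be in the model regardless of bivariate p value; other exposures enter at bivariate p<0.1. Inference is limited to these two practices.

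The existing sentence on the 0.1 threshold must be removed or qualified so that it does not contradict this. The 0.05 significance cutoff is unaffected.

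The cost is wording and one parameter for practice. Data collection and the stated sample size do not change. Loss of precision is negligible: at 250 per practice, RMSE for fixed versus random effect is 0.227 versus 0.221 at OR 1.2 and 0.227 versus 0.232 at OR 1.5. Conclusions would not extend beyond these two practices, but the current model offers little basis for that either.

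### Aim 1 tests an unlisted set of exposures at an unadjusted p<0.05 with no primary exposure, and its 0.1 screen can drop altruism from the model (minor; cheap to improve)

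*Combined protocol and SAP*

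**What the plan says.** Under Objectives, Specific Aim 1 is "To identify associations with influenza vaccine hesitancy, including parental demographics and altruism score", in families at two pediatric practices. The list is open-ended. The Analytical Plan makes dichotomised hesitancy the primary outcome, and the exposures "include general demographic and clinical characteristics along with the Self-Report Altruism Scale". The one specific clinical item is a medical complexity category. Interventions and Interactions mentions several demographic questions without listing them, and Subject Recruitment Methods adds further demographic data from chart review.

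The procedure has two steps. First, "Associations between hesitancy and potential exposures will be assessed using chi square or ANOVA". Associations that pass then enter a mixed-effects logistic model with practice as a random effect. One sentence sets both thresholds: "A p value of 0.1 will be used for inclusion of variables in the model; otherwise, a p value <0.05 will be the cutoff for" declaring a result significant.

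Altruism is singled out in the Objectives, which say that the intervention's effectiveness depends on it and that "we also seek to determine if there is an association between parental altruism and vaccine hesitancy for their children". The Analytical Plan gives it no special status.

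Under Sample Size, Aim 1 has its own power statement: 25% baseline hesitancy, a meaningful difference given as 15%, 80% power and 250 subjects per group. The groups are not named.

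**The concern.** Aim 1 fixes one outcome but no primary contrast. Every exposure that reaches p<0.05 can be reported as associated with hesitancy, and a chance demographic finding would carry the same weight as the altruism result. A reader could not tell the planned answer from the most favourable of several looks, and would not know how many looks there were.

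The second difficulty is the screen. If the altruism score has a bivariate p value above 0.1, the written procedure never estimates its adjusted association, although that is the relationship the study most needs to describe.

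**Working it through.** **1. The plan's own figure.** The 250 per group reproduces as one comparison of 25% with 15% at two-sided 0.05 and 80% power (sidedness is not stated; pooled-variance formula, no continuity correction):

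n = [1.960·√(2·0.20·0.80) + 0.842·√(0.25·0.75 + 0.15·0.85)]² / 0.10² = (1.109 + 0.472)² / 0.01 ≈ 250.

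Of the variants tried, only this one gives 250. One-sided gives 197 and continuity-corrected gives 270. A literal 15-point difference gives 100 (25% vs 10%) or 152 (25% vs 40%). So the sample size presupposes a single unadjusted comparison, which the plan does not identify.

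**2. Size of the family.** The documents give no number. The Analytical Plan names two specific exposures (altruism and medical complexity) plus general demographic and clinical characteristics. The ranges below assume k = 3, 5 or 10.

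**3. Independent exposures, none associated with hesitancy.** P(at least one p<0.05) = 1 − 0.95^k:

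- k = 3: 1 − 0.857 = 14.3%
- k = 5: 1 − 0.774 = 22.6%
- k = 10: 1 − 0.599 = 40.1%

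**4. The two-step procedure, simulated.** Settings: 500 subjects (2 × 250), 25% hesitant, no true association, bivariate screen at 0.1, then a joint logistic model read at 0.05; 4,000 replicates per setting, practice effect omitted. Exposures were either all continuous, or one continuous and the rest dichotomised from correlated normal variables.

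| k | 1 − 0.95^k | Final model, correlation 0 | Final model, correlation 0.5 |
|---|---|---|---|
| 3 | 14% | 14% | 9–11% |
| 5 | 23% | 22–23% | 10–15% |
| 10 | 40% | 39–41% | 12–20% |

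The ranges at correlation 0.5 mainly reflect the type of exposure. The lower end is for all-continuous exposures; dichotomising weakens the correlation and raises the rate. At correlation 0 the screened rate matches the unscreened one, so the screen neither adds to nor removes the multiplicity.

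**5. Cost of the alternatives.** Bonferroni over 5 exposures (0.01 each) cuts power at 250 per group from 80.0% to 58.7%, and 373 per group would be needed for 80%. Over 10 exposures (0.005 each) the figures are 49.5% and 425. Naming one primary exposure keeps 0.05 for it and loses no power to adjustment.

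**The case against.** The best defence is that Aim 1 is a baseline search for correlates within a single-arm study of a pilot intervention. It makes no efficacy claim, and unadjusted p values are common in such work. This stands: formal family-wise control is not obligatory, and the point is about naming and labelling.

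A second defence is that the Objectives use the verb *explore* for hesitancy and altruism, so an exploratory intent is already on record. This stands in part. The wording covers altruism only, not the demographic and clinical family. The section labelled Exploratory Aim is limited in the Analytical Plan to qualitative interview data, while Aim 1 is a Specific Aim with a power statement.

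Third, the 0.05 cutoff may be meant for the final model only. The final-model column in the working takes that narrower reading, and the rates still exceed 5%.

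Three stronger readings are tempting but unsupported:

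- A reader might infer that the plan breaches a promised 5% error rate for Aim 1 as a whole. It states a per-test cutoff and promises nothing family-wise.
- A reader might infer that a false Aim 1 finding would misdirect targeting of the intervention, because the Background speaks of a subpopulation "based on baseline altruism score, race, educational level, or political affiliation". That sentence concerns response to the intervention, not correlates of baseline hesitancy. Nor does it fix the Aim 1 exposure list.
- A reader might infer that screening at 0.1 and then testing at 0.05 itself inflates the error. The simulation at correlation 0 shows that it does not.

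**Conclusion.** The point holds as a minor one. Aim 1 has no closed exposure list, no primary exposure and no statement that its p values are unadjusted, and the exposure central to the rationale can be screened out. The false-association rates in the working run from about 9% (3 exposures, correlation 0.5, final model) to about 40% (10 independent exposures). They rest on an assumed number of exposures, on no exposure being truly associated, and on a simulation without the practice effect, so they show scale and do not predict a rate for this study. What the change improves is how Aim 1 can be read: one planned answer about altruism, and a set of labelled leads.

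**What to change.** In the Aim 1 paragraph of the Analytical Plan:

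- Name the Self-Report Altruism Scale score as the primary exposure. Enter it in the mixed-effects logistic model regardless of the 0.1 screen, and test its adjusted association at two-sided 0.05.
- List the other demographic and clinical exposures. Report them as exploratory, with estimates, 95% confidence intervals and a statement that their p values are unadjusted. Apply a Holm adjustment over that list only if claims of significance are wanted.

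Under Sample Size, state which two-group comparison the 250 per group refers to. Altruism is analysed as a continuous score from 20 to 100, so the present statement does not give the power of its test.

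The cost is a few sentences, with no new data or subjects. The downside is that a demographic association just under 0.05 would be reported as hypothesis-generating and not as established, although demographics are part of the stated objective.
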